Video-assisted thoracic surgery (VATS) has the advantages of small operation wound, quick postoperative recovery and few complications. Currently, it has gradually replaced the traditional thoracotomy. VATS usually requires one-lung ventilation (OLV) on the non-surgical side of the lung using a double-lumen bronchial catheter. One-lung ventilation refers to a ventilation technique that separates the two ventilation pathways at the level of the tracheal carina, with the aim of causing the surgical side of the lung lobe to collapse and protecting the non-surgical side of the lung lobe from contamination. At the same time, it is more conducive to the exposure of the surgical field and reduces the incidence of surgical complications. During one-lung ventilation, various pathophysiological changes may occur due to mechanical injury, lung collapse, imbalance of the ventilator-blood flow ratio in the lungs, ischemia-reperfusion, etc., leading to the release of a large amount of inflammatory factors, local and systemic inflammatory responses, affecting perioperative oxygenation, and causing hypoxemia or even lung injury. During the OLV process, although the collapsed lung is not ventilated, blood still flows through it. This can lead to an imbalance in the Ventilation/perfusion ratio (V/Q), resulting in an increase in intrapulmonary shunt and a decrease in oxygenation, which in turn causes hypoxemia. Secondly, thoracic surgeries are generally performed in a lateral position. Due to the influence of gravity, the distribution of ventilation and blood flow in patients is uneven, with the maximum shunt volume reaching 40-50%. Finally also causes longitudinal partition by gravity, the heart to move to the contralateral lung, make limited ventilation side lung ventilation, airway will also appear, blood flow ratio, leads to increase in patients with pulmonary shunt.

Hypoxic pulmonary vasoconstriction (HPV) is a unique adaptive mechanism of the pulmonary circulation, which can promote the flow of blood from hypoxic alveolar areas to well-ventilated alveolar areas, thereby improving V/Q dysregulation. When the partial pressure of oxygen in the alveoli decreases, it can trigger HPV, causing the small arteries before the capillaries in the hypoxic area of the lungs to contract, increasing vascular resistance and reducing blood flow. As a result, more blood flows to the well-

ventilated alveolar area, thereby reducing the shunt within the lungs. Many factors such as anesthetic drugs, acid-base imbalance, temperature, vasodilators and pulmonary operations may all affect the HPV mechanism in non-ventilated lungs. Alveolar hypoxia stimulates the production of various vasoactive substances, such as peptide endothelin, thromboxane A, platelet activating factor and leukotrienes, all of which have strong vasoconstrictive effects. Many drugs used during the anesthesia period can inhibit HPV. All volatile anesthetics inhibit HPV in a dose-dependent manner. Therefore, the inhibition of HPV is one of the main reasons for hypoxemia during OLV. The oxygen delivery of anesthetics during OLA is very complex and depends on hemoglobin, oxygen saturation and cardiac output. The oxygen delivery volume must exceed the oxygen consumption; otherwise, cellular hypoxia will occur.

Hypoxemia related to OLV is mainly attributed to shunt, shunt will improve over time. Unless auxiliary measures are taken or bilateral lung ventilation is restored, shunt will remain fixed. The oxygen transport mainly depends on the concentration of the hemoglobin in the blood, hemoglobin saturation degree and output. The reduction of any one of them will decrease oxygen delivery and may lead to target organ dysfunction, increasing the risk of complications such as cognitive dysfunction, atrial fibrillation, renal failure and pulmonary hypertension in patients during the perioperative period [9-10].

Epidemiological investigations have found that approximately 50% of elderly people worldwide have undergone at least one surgical treatment. POCD is one of the common postoperative complications. Compared with younger patients, the risk of adverse reactions in patients over 60 years old is significantly higher, and about one quarter of patients may develop POCD. With the increase of age, the number of brain neurons decreases, neurotransmitters change, the ability to regulate cerebral blood flow reduces, liver and kidney functions decline, the clearance of anesthetic drugs decreases, intraoperative blood loss increases, and postoperative infections all lead to a significant increase in the incidence of POCD in elderly patients [12]. POCD is acute and reversible. The current pathogenesis remains unclear. Elderly patients are an independent risk factor for POCD. Other risk factors include low education level, prolonged anesthesia time, postoperative co-infection, previous cerebral vascular disease or cognitive decline, etc. Early prevention can significantly reduce postoperative cognitive impairment in elderly patients. With the prolongation of postoperative recovery time, the decline in cognitive function in most patients can gradually alleviate or disappear, while in a small number of patients, it may persist and progressively worsen [13].

Thoracic surgery can promote the production of pro-inflammatory factors and reactive oxygen species (ROS) due to intense hemodynamic fluctuations and the occurrence of hypoxemia, leading to the proliferation of glial cells in the brain. Increased oxidative stress

and inflammation injury will destroy the function of endothelial cells, lead to the blood-brain barrier (BBB) permeability increases, nerve vascular decouple and cerebral blood flow decreases, nutrient transport and toxic product removal was damaged and eventually lead to white matter damage, nerve degeneration and cognitive obstacle [14].

In order to improve hemodynamic stability and the occurrence of hypoxemia during thoracoscopic surgery in elderly patients and thereby improve postoperative cognitive dysfunction, more rigorous anesthesia methods and medications should be adopted to reduce the incidence of hypoxemia and POCD. At present, the application of drug intervention is a hot topic in the research on improving hypoxemia and postoperative cognitive dysfunction during thoracoscopic surgery for OLV.

Remimazolam, as a short-acting γ -aminobutyric acid (GABA)-A receptor agonist with rapid onset and metabolism, has metabolites that have almost no pharmacological activity, reducing the risk of drug accumulation. At the same time, it has obvious hemodynamic and respiratory stability. Remimazolam has the advantages of rapid onset, fast metabolism, no dependence on liver and kidney functions, no accumulation, and less impact on circulatory function. It is very suitable to be used as a sedative drug during anesthesia induction and maintenance in elderly patients [15-17]. At present, most of the research on remimazolam at home and abroad focuses on short surgeries and outpatient painless gastroscopy and colonoscopy, etc. There is a lack of relevant research on the application of remimazolam in the perioperative period of elderly patients. Liao et al. [18] found that remimazolam and dexmedetomidine are equally beneficial in reducing the incidence of early postoperative POCD in elderly patients undergoing radical gastrectomy for gastric cancer. The underlying mechanism is to reduce the occurrence of inflammatory responses. Previous studies have shown that remimazolam is used for general anesthesia induction and maintenance for elderly patients undergoing thoracoscopic lobectomy can alleviate brain injury in the elderly and thereby reduce the incidence of POCD [19]. However, whether remimazolam can reduce the occurrence of POCD by improving interpulmonary oxygenation during one-lung ventilation in elderly patients undergoing thoracoscopic lobectomy has not been studied at home or abroad so far.

This project mainly explores the effects of remimazolam mesylate on oxygenation and intrapulmonary shunt in elderly patients during one-lung ventilation after thoracoscopic surgery, as well as its impact on postoperative cognitive dysfunction. To clarify the application advantages of remimazolam toluenesulfonate in thoracoscopic surgery for elderly patients, and to provide new clinical application references for improving oxygenation during one-lung ventilation and postoperative cognitive dysfunction in elderly patients undergoing thoracoscopic surgery.

and pulmonary dynamic compliance (Cdyn) were calculated. ④ Serological indicators: 4mL of peripheral venous blood was collected from the patient immediately after the operation (T6) and 24 hours after the operation (T7). The serum central nervous system specific protein (S100 β) was detected by enzyme-linked immunosorbent assay (ELISA). Levels of interleukin-6 (IL-6) and interleukin-8 (IL-8). The white blood cell count, the percentage of neutrophils, the percentage of lymphocytes and C-reactive protein (CRP) in the peripheral blood of the patients were detected. ⑤ Postoperative recovery: The Ramsay sedation classification was used to assess the awakening status at 2, 4, 12, and 24 hours after the operation. The pain conditions at 2, 4, 12 and 24 hours after the operation were evaluated by VAS score, and the number of cases of postoperative remedial analgesia in each group of patients was recorded. Record the occurrence of postoperative adverse reactions such as restlessness, nausea and vomiting, dizziness, arrhythmia and drowsiness in each group of patients; Record the occurrence of postoperative pulmonary complications such as pulmonary infection, respiratory failure and atelectasis within one week after the operation; The postoperative recovery quality of patients was evaluated by the QOR-15 scale at 24 hours and 48 hours after the operation. Record the duration of the patient's postoperative hospital stay. Finally, the collected data will be statistically analyzed and compared.

III. Research Design

1.selective cases :

1.1 Inclusion criteria for cases:

- 1) Patients aged 65 to 75 years who are scheduled to undergo thoracoscopic surgery under general anesthesia
- 2) BMI 18~30 kg/m²;
- 3) ASA is classified into grades I to III;
- 4) There are no contraindications to the relevant drugs;
- 5) Both the patients and their families agreed to participate in this study and signed the informed consent form.

1.2 exclusion criteria:

- 6) Patients with severe sinus bradycardia (heart rate <50 beats per minute) and atrioventricular block;
- 7) Respiratory tract infection and the use of non-steroidal anti-inflammatory drugs or hormone drugs within two weeks before the operation;
- 8) People with central nervous system and mental disorders;
- 9) In the past half year, I have taken anticholinergic drugs, anticonvulsants, anti-anxiety drugs, antidepressants, etc;
- 10) Severe liver and kidney dysfunction and immune system diseases, uncontrolled hypertension and diabetes;
- 11) History of preoperative radiotherapy and chemotherapy;
- 12) Patients with communication barriers who are unable to cooperate to complete the test.

1.3 Exclusion Criteria:

- 13) Patients with OLV<60 minutes or those who are converted to thoracotomy;
- 14) Intraoperative blood loss >1000ml;
- 15) (3) Patients transferred to the ICU after surgery;

2. Test Method

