2.3 Preoperative Preparation

One day before the operation, the patient was visited to have a comprehensive and detailed understanding of the patient's current physiological and pathological conditions, as well as to assess the patient's cardiopulmonary function before the operation. The application of remimazolam mesylate in anesthesia was also explained to the patient. Explain the precautions for the hand surgery, and fast for 8 hours and refrain from drinking for 6 hours. Sign the informed consent form for anesthesia and the "Informed Consent Form" for the clinical trial.

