3.1 General Condition of the Patient

Age, gender, ASA classification, BMI, surgical method, surgical side, preoperative basic lung function

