3.5 Serological indicators

4mL of peripheral venous blood was collected from the patients at the time of entering the room (T0), before extubation (T4), and 24 hours after the operation (T6). The levels of serum central nervous system specific protein (S100 β) and interleukin-6 (IL-6) were detected by enzyme-linked immunosorbent assay (ELISA). Detect the white blood cell count, the percentage of neutrophils, the percentage of lymphocytes, and C-reactive protein (CRP) in the peripheral blood of the patients.

3.6 Postoperative Follow-up:

Postoperatively, Ramsay sedation scale was used to assess the recovery at 2, 4, 12 and 24 hours after surgery; VAS score was used to evaluate the pain at 2, 4, 12 and 24 hours after surgery. The number of cases requiring rescue analgesia in each group was recorded. The occurrence of postoperative adverse reactions such as restlessness, nausea and vomiting, dizziness, arrhythmia and drowsiness was recorded. The occurrence of PPCs such as pulmonary infection, respiratory failure and atelectasis within one week after surgery was recorded. The QOR-15 scale was used to assess the postoperative recovery quality at 24 and 48 hours after surgery. The postoperative hospital stay of patients was recorded.

PPCs can be diagnosed if any of the following conditions are met, in accordance with the European Perioperative Clinical Outcome (EPCO) standards jointly issued by the European Society of Anaesthesiology and the European Society of Intensive Care Medicine: (1) Pulmonary infection, suspected respiratory system infection and treated with antibiotics, and at least one of the following is met: new or changed sputum, new or progressive pulmonary infiltration shadow, fever, total white blood cell count $> 12 \times 10^9/L$. (2) Respiratory failure, $\text{PaO}_2 < 60 \text{ mmHg}$ when breathing air, $\text{PaO}_2/\text{FiO}_2 < 300 \text{ mmHg}$ or $\text{SpO}_2 < 90\%$, requiring oxygen therapy. (3) Pleural effusion confirmed by imaging. (4) Atelectasis confirmed by imaging. (5) Pneumothorax confirmed by imaging. (6) Bronchospasm, new wheezing heard and requiring treatment with bronchodilators. (7) Aspiration pneumonia: acute lung injury after aspiration of gastric contents.

IV. Statistical Analysis

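### POCD is a stated aim, but Sections 2.3 and 3.1-3.6 schedule no cognitive measure, and the two serology lists contradict each other on time points, the T6 label and IL-8

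*Protocol*

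**What the plan says.** **Aim.** The background and objective text of the Protocol gives as the open question "whether remimazolam can reduce the occurrence of POCD by improving interpulmonary oxygenation during one-lung ventilation", and the project is to study oxygenation and shunt "as well as its impact on postoperative cognitive dysfunction".

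**Before surgery.** The visit in Section 2.3 reviews the patient's general condition, "as well as to assess the patient's cardiopulmonary function before the operation". Section 3.1 records "Age, gender, ASA classification, BMI, surgical method, surgical side, preoperative basic lung function".

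**After surgery.** Section 3.6 and item 5 of the outcome list before III. Research Design name the same measures: Ramsay, VAS, rescue analgesia, adverse reactions, pulmonary complications, QoR-15 and hospital stay. Item 5 ends its scales with "The postoperative recovery quality of patients was evaluated by the QOR-15 scale at 24 hours and 48 hours after the operation". Section 3.6 then defines pulmonary complications in detail, starting with "PPCs can be diagnosed if any of the following conditions are met" and listing seven conditions. It has no counterpart for POCD.

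**Serology.** Item 4 of the outcome list draws blood "immediately after the operation (T6) and 24 hours after the operation (T7") and includes IL-8. Section 3.5 draws it "at the time of entering the room (T0), before extubation (T4), and 24 hours after the operation (T6") and does not include IL-8. Both are current text.

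**Analysis.** Section IV compares groups on continuous data by t-test or rank sum test. It mentions no baseline adjustment.

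**The concern.** An aim needs a measurement. If Section 3 is followed as written, the trial collects S100β, IL-6, blood counts and CRP, but nothing that observes cognition. Any statement about POCD would then rest on markers alone. An analysis plan cannot repair this, because a preoperative cognitive score that was never taken cannot be recovered later.

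The serology conflict falls on S100β, the only central nervous system marker in the visible text. A value filed as T6 may come from the end of surgery or from 24 h. Whether a baseline sample or any IL-8 result exists depends on which list staff follow.

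**Working it through.** **1. Cognitive measures in the visible schedule**

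| Place | Content | Cognitive measure |
|---|---|---|
| 2.3 | general condition, cardiopulmonary function | none |
| 3.1 | demographics, ASA, BMI, surgery, lung function | none |
| 3.2-3.4 | intraoperative data, haemodynamics, blood gases | none |
| 3.5 | S100β, IL-6, blood counts, CRP | none (markers) |
| 3.6 and item 5 | Ramsay (4 times), VAS (4 times), QoR-15 (2 times), events, hospital stay | none |

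Ramsay grades sedation, VAS pain, and QoR-15 quality of recovery. The count of cognitive assessments in these sections is 0. Exclusion criterion 12 refers to completing a test, but names no instrument and schedules none.

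**2. The serology lists side by side**

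| | Outcome list, item 4 | Section 3.5 |
|---|---|---|
| Entering the room | not listed | T0 |
| Before extubation | not listed | T4 |
| Immediately after surgery | T6 | not listed |
| 24 h | T7 | T6 |
| IL-8 | yes | no |

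Four distinct times appear and one (24 h) is common, under two labels.

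Inputs from Section IV and Section 2.2: 50 per group, 3 groups. Patients: 3 × 50 = 150.
- Draws: 150 × 2 = 300 against 150 × 3 = 450.
- Volume per patient, reading 4 mL as per draw: 2 × 4 = 8 mL against 3 × 4 = 12 mL.
- IL-8 results: 150 × 2 = 300 against 0.

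**3. What a T0 sample could add**

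For a comparison of 24 h values adjusted for T0, the variance relative to the unadjusted comparison is about 1 − ρ², where ρ is the T0-to-24 h correlation within groups. The Protocol gives no ρ, so a range is assumed:
- ρ = 0.3: 1 − 0.09 = 0.91, variance 9% lower, standard error × 0.954
- ρ = 0.5: 1 − 0.25 = 0.75, variance 25% lower, standard error × 0.866
- ρ = 0.7: 1 − 0.49 = 0.51, variance 49% lower, standard error × 0.714

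The Protocol states no figure of its own on any of these points, so there is none to reproduce.

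**The case against.** **The missing text may hold the test.** The outcome list becomes visible partway through item 3; items 1, 2 and part of 3 cannot be read. A reader might infer that the trial has no cognitive test at all. The documents do not support that: a test may be named in the unseen items, and exclusion criterion 12 is compatible with one. What stands is narrower. The data-collection sections, which are visible, contain none, so they fail either the aim or the outcome list.

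**Label order.** A reader might add that T6 in item 4 falls before T4 and T5, because patients leave theatre intubated. That applies the labels of Section 3.3 to a list whose own T0-T5 are not visible and which labels 24 h differently. It cannot be shown, and the contradiction does not need it.

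**Bias.** A reader might infer either that the conflict biases the 24 h comparison or that this comparison is safely unbiased. Neither follows. Both lists include the 24 h sample, so the choice of list does not itself bias it. But Section 1.3 removes patients for events during or after surgery (short one-lung ventilation, conversion, heavy blood loss, ICU transfer), so freedom from bias cannot be asserted.

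**Adjustment belongs in the analysis plan.** This is largely fair. Section IV gives generic tests and does not mention S100β, and an unseen plan may go further. Adjustment is therefore offered as an improvement where Section IV names only unadjusted tests, not as the correction of an error.

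**Conclusion.** The point holds in two limited parts. First, POCD is an aim for which Sections 2.3 and 3.1-3.6 schedule 0 assessments, no baseline and no definition. Whether the unseen start of the outcome list names a test is unknown, but reconciliation is needed in either case. Second, the serology lists contradict each other outright: 1 of 4 times shared, T6 with two meanings, 2 or 3 draws per patient, and IL-8 in one list only.

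The gain from T0 adjustment, a 9% to 49% lower variance, rests wholly on the assumed correlations of 0.3 to 0.7. The primary endpoint (oxygenation index at T3) and the sample size of 50 per group are untouched. The matter should be corrected, but it does not threaten the main comparison.

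**What to change.** 1. Reconcile Section 3 with the outcome list. If a cognitive test is already named there, carry it into 2.3 (baseline) and 3.6 (follow-up), with its time points and a definition of POCD. Otherwise limit the objective and the conclusions to S100β and inflammatory markers, and make no claim about POCD.
2. Merge the two serology lists into one schedule, with one label per time point and a single decision on IL-8.
3. If the T0 sample of Section 3.5 is kept, compare 24 h S100β and IL-6 between groups adjusted for the T0 value (log scale if skewed), with a confidence interval, in place of the unadjusted tests in Section IV.

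**Cost.** Narrowing the aim, relabelling and the adjusted comparison are text edits; the price is a narrower claim. If 3.5 is the operative schedule, no new sample is needed. If the outcome list is operative, keeping T0 adds one 4 mL draw per patient, 150 in all. A cognitive test carried into Section 3 means at least two assessments per patient, 150 × 2 = 300, plus staff time.

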2.2 Experimental Subjects

The patients were randomly divided into 3 groups according to the random number table method:

Remimazolam group (Group R): After intubation, remimazolam was maintained at a pump rate of 1-2 mg/kg/h until 10 minutes before the end of the operation.

Propofol group (Group P): After intubation, propofol was maintained at a pump rate of 4-10mg/kg/h until 10 minutes before the end of the operation.

Remimazolam combined with propofol group (Group C): After intubation, remimazolam at a dose of 0.3-1mg/kg/h and propofol at a dose of 3-6 mg/kg/h were maintained until 10 minutes before the end of the operation.

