2.5 Anesthesia induction and maintenance

After the pre-anesthesia preparations were completed, anesthesia induction began. After 3 minutes of mask inhalation of pure oxygen, the three groups were successively given fentanyl 3-5 μ g/kg, etomidate 0.4 mg/kg, and cisatracurium 0.15 mg/kg. After mask controlled oxygen inhalation for 5 minutes, after the relaxation of the mandibular muscles and anesthesia induction, a double-lumen endobronchial tube (DLT) was inserted to ensure good alignment. The anesthesia machine was adjusted to volume-controlled ventilation, and the respiratory parameters were adjusted: the tidal volume was regulated by 6-8 ml/kg and the respiratory rate was maintained to keep the end-expiratory CO₂ partial pressure at 35-45

mmHg. After the anesthesia stabilizes, a retrograde puncture and catheterization of the internal jugular vein is performed. The puncture point beside the thyroid cartilage is determined. After disinfection and laying a towel, the puncture is performed and a catheter is placed. The catheter is fixed with sutures and fluid replacement is carried out during the operation. Anesthesia maintenance: Total intravenous anesthesia was used during the operation. Intravenous anesthetics were continuously pumped according to the groups. Group R: Remimazolam was maintained at a pumping rate of 1-2mg/kg/h. Group P: Propofol was maintained at a pump speed of 4-10mg/kg/h. Group C: Maintained with remimazolam at a dose of 0.3-1mg/kg/h and propofol at a dose of 3-6 mg/kg/h. All three groups were combined with remifentanil at 6-12 μ g/kg/h, and the drug pumping speed was adjusted to maintain the BIS value at 40-60. Thirty minutes before the end of the operation, 0.15 mg/kg dezocine was administered. The infusion of remimazolam and propofol was stopped 10 minutes before the operation, and remifentanil was stopped 5 minutes before the operation.

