2.6 Anesthesia Completed

After the anesthesia ended, all patients underwent lung recruitment for 30 seconds after bilateral lung ventilation was restored. The patient was sent to the PACU with a tube. After spontaneous breathing, muscle strength and consciousness were restored, sputum was suctioned and the tube was removed. The patient will be returned to the ward after assessment by the PACU physician.

3. Data collection

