3.2 Intraoperative condition of the patient

One-lung ventilation time, blood loss, infusion volume, dosage of remimazolam, dosage of propofol, dosage of remifentanil, urine volume, blood loss, dosage of ephedrine, dosage of atropine, occurrence of hypoxemia

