3.3 Cardiovascular responses of patients at all times during the perioperative period

Record the heart rate, mean arterial pressure and pulse oxygen saturation of the patient at the time of entering the room (TO), before OLV (T1), 30 minutes after OLV (T2), 60 minutes after OLV (T3), before extubation (T4), and 5 minutes after extubation (T5).

3.4 Intraoperative blood gas analysis:

All patients underwent arterial blood gas analysis and central venous blood gas analysis before OLV (T1), 30 minutes after OLV (T2), and 60 minutes after OLV (T3). Record the Pplat, VT, PEEP, OI, PaO₂, PAO₂, PcvO₂, SaO₂, ScvO₂, (A-a)DO₂, RI at these three moments, and calculate Qs/Qt and Cdyn.

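### Section 1.3 removes patients already randomised and treated because of later events; the ICU rule discards a primary value normally already measured and can hide severe complications

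*Protocol*

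**What the plan says.** Section 1.2 lists the exclusions that can be checked before surgery. Section 1.3, under a near-identical heading, adds three more: "Patients with OLV<60 minutes or those who are converted to thoracotomy", intraoperative blood loss above 1000 ml, and "Patients transferred to the ICU after surgery".

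Section 2.2 states that "The patients were randomly divided into 3 groups according to the random number table method" and starts each group's maintenance drug after intubation. Section 2.5 confirms this for the operation itself: "Intravenous anesthetics were continuously pumped according to the groups". The planned route after surgery is given in 2.6: "The patient was sent to the PACU with a tube".

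Blood gases are taken "before OLV (T1), 30 minutes after OLV (T2), and 60 minutes after OLV (T3" (section 3.4), and section IV names the oxygenation index at T3 as the main endpoint, with a 50 mmHg non-inferiority margin. Section 3.6 collects pulmonary complications over one week (respiratory failure among them), adverse reactions, QoR-15 and postoperative hospital stay. Nothing in the protocol says that a patient who meets 1.3 stays in any analysis, is replaced, or counts towards the 20% dropout and withdrawal allowance.

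**The concern.** None of the 1.3 events can be known at enrolment. They are removals after treatment, labelled as eligibility criteria, and the assigned drug could influence them. Removing patients on that basis gives up the protection of randomisation.

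The rules do not all do the same damage:

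- **ICU transfer.** The decision comes after surgery, when T3 has normally been measured. A valid primary value is discarded because of something that happened later, and the patient also leaves the complication, recovery and hospital-stay comparisons, where the most severe cases matter most.
- **Conversion and heavy blood loss.** These may come before or after T3, so some measured values may be lost. The protocol does not link either event to oxygenation.
- **OLV under 60 minutes.** No T3 exists. Dropping these patients distorts T3 only if OLV was cut short because of poor oxygenation. Section 3.2 records "One-lung ventilation time, blood loss, infusion volume" and "dosage of atropine, occurrence of hypoxemia", and T2 gives a blood gas, so this can be examined in part. The reason OLV ended is not a listed item. Section 1.1 sets no planned OLV duration, so short operations can be enrolled and then removed.

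In a non-inferiority comparison, losing more low-oxygenation patients from the study group moves the T3 difference towards zero and makes non-inferiority easier to declare.

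**Working it through.** **Order of events.** Allocation, then infusion after intubation (2.2, 2.5), then T1, T2 and T3 (3.4), then end of surgery, then PACU or ICU (2.6, 1.3). Any patient with at least 60 minutes of OLV reaches T3 before ICU transfer is possible.

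**The plan's own figures (section IV).** Margin 50, α = 0.025 (read as one-sided), power 0.80, 38 per group, 20% loss, final 50 per group.

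- Inflation: 38/(1 − 0.20) = 47.5, rounded up to 48, close to the stated 50.
- No SD is given, so 38 cannot be checked directly. Solving back with the normal formula: SD = 50 × √(38/2)/(1.960 + 0.842) = 77.8. With the noncentral t it is 76.8. SD 77 is used below.

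**Effect on the T3 test.** Assumptions: 50 per group, a true deficit equal to the margin (175 vs 125 mmHg), and oxygenation-related removals drawn evenly from the lower half of the patient's own group. The removal rates are assumed, because the protocol gives none. Each case is 100,000 simulated trials with a pooled t interval. Entries are one-sided error for gamma / normal data; the nominal value is 0.025.

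| Removed: control vs study | Half of removals related | All related |
|---|---|---|
| 2% vs 6% | 0.028 / 0.030 | 0.034 / 0.036 |
| 5% vs 10% | 0.030 / 0.033 | 0.037 / 0.042 |
| 10% vs 20% | 0.041 / 0.044 | 0.065 / 0.075 |
| 10% vs 5% (reversed) | 0.017 / 0.019 | 0.013 / 0.015 |
| 20% vs 10% (reversed) | 0.012 / 0.013 | 0.006 / 0.007 |

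Reference cases: no removal, 0.023 / 0.025; removal unrelated to oxygenation, 0.024 / 0.025; related removal at equal rates (5%, 10% or 20% in both groups), 0.022 to 0.025.

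**Hand check (normal data, 10% vs 20%, all related).** The lower half of a normal distribution averages 0.798 × 77 = 61.4 below the mean. Removing a fraction p from it raises the remaining mean by 61.4 × p/(1 − p).

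- Study group: 61.4 × 0.20/0.80 = 15.4. Control: 61.4 × 0.10/0.90 = 6.8.
- The difference moves from −50 to about −41.5, a shift of 8.5 mmHg.
- With 40 and 45 analysed, SE = 77 × √(1/40 + 1/45) = 16.7, and 8.5/16.7 = 0.51.
- The error is the upper tail beyond 1.96 − 0.51 = 1.45, about 0.074, in line with the simulated 0.075. Fixing the number removed in each trial, instead of letting it vary by chance, gave 0.064.

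**ICU rule alone on T3.** If ICU patients' T3 is lower than that of the other patients by d, the bias is d × (study ICU rate − control ICU rate). For 10% vs 5% and d = 50 to 100 mmHg (assumed), it is 2.5 to 5 mmHg. At equal rates and equal d it is zero.

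**Pulmonary complications (assumed counts, 50 per group).** One case removed: 5/50 = 10.0% becomes 4/49 = 8.2%. With a true 10/50 (20%) vs 5/50 (10%), removing 4 vs 1 ICU cases that all had a complication leaves 6/46 (13.0%) vs 4/49 (8.2%). Removing 5 vs 0 leaves 5/45 (11.1%) vs 5/50 (10.0%).

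**The case against.** The strongest reply is that the T3 effect is hypothetical. Removal related to oxygenation does not inflate the error unless the groups lose unequally, and nothing in the protocol suggests that they will. This is correct, as the equal-rate results show. The 0.075 figure needs one group to use the whole 20% allowance, the other half of it, and every removal to be tied to low oxygenation. The table covers removals of any kind; the effect of ICU transfer alone is likely to be small against 50 mmHg. The T3 figures are therefore illustration, not prediction.

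The ICU wording is also undefined. If it means only direct transfer in place of the PACU, a complication that develops later on the ward stays in the count, and the loss is smaller. Early respiratory failure leading to direct transfer would still be lost.

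If 1.3 removals fall within the 20% allowance, power is covered up to that rate, which leaves possible bias as the issue.

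Finally, analysis sets and missing-data methods are commonly left to an SAP, and a per-protocol set is a usual companion in a non-inferiority trial. That holds for how to handle a missing T3 and for keeping a per-protocol analysis. It does not rescue 1.3: the protocol states an exclusion, and an SAP that kept these patients would contradict it. Reading the heading as withdrawal criteria leads to the same result.

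**Conclusion.** The concern holds and should be fixed. That the 1.3 rules act after treatment, and that the ICU rule discards a T3 normally already measured, follows from the protocol's own order of events and needs no assumption about rates. So does the exposure of postoperative outcomes to the loss of severe cases, although its extent depends on how ICU transfer is defined.

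The size of any T3 bias cannot be computed from the document. Over the assumed range (SD 77, 2% vs 6% up to 10% vs 20% removed), one-sided error is 0.028 to 0.075 when the study group loses more low-oxygenation patients and 0.006 to 0.019 when the control group does. It stays at about 0.025 when loss is equal or unrelated to oxygenation. The link from ICU transfer to low intraoperative oxygenation is an inference. The complication comparison is affected more directly: about 1.8 percentage points for each case removed from a group with 5/50.

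**What to change.** 1. Stop using section 1.3 as an exclusion from the main analysis.
2. Add a planned OLV of at least 60 minutes to the inclusion criteria in 1.1.
3. Define the main analysis as all randomised patients in the three groups who received study drug. Keep every measured T3, including those of ICU, converted and high-blood-loss patients, and follow all of them for pulmonary complications, adverse reactions, QoR-15 and hospital stay.
4. Add one data item: why OLV ended before 60 minutes.
5. Keep the 1.3 population as a per-protocol sensitivity analysis, and say whether ICU transfer means direct transfer or any later admission.
6. Leave the method for a missing T3 to the SAP, provided it is prespecified and does not favour non-inferiority.

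The cost is amendment wording, one data item, one more analysis set and continued follow-up of the affected patients. The sample size does not change, and data are gained: at SD 77, power is 0.82 with 40 analysed per group, 0.86 with 45 and 0.90 with 50.

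The change cannot restore a T3 that was never taken. If half of those removed have a T3 that is now kept and the rest stay missing, the all-related error falls from 0.065 / 0.075 to 0.037 / 0.042 (10% vs 20%) and from 0.037 / 0.042 to 0.029 / 0.032 (5% vs 10%). What remains depends on the SAP's missing-data method.
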